9.5. Premature Termination and Missing Values

Subjects may be withdrawn from the study prematurely for lost to follow-up, withdrawal the consent or other conditions as mentioned in Section 4.5.4. The reason of premature termination will be summarized. For drop-out subjects, the listing table will list the detailed reason and date for patients' withdrawals. For subjects who terminate study drug early, values measured after termination of study drug will be censored.

Last observation carried forward (LOCF) will be used to approach the missing data of primary endpoint in ITT population. No missing data will be imputed for the secondary efficacy or safety analyses.

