6.2.3. On treatment visits (Day 29±3, Day 57±3, Day 85±3)

During the treatment period, subjects will visit the clinic every 4 weeks. Subjects have to come in fasted state for all visits. Therefore, subjects will be instructed not to take study drug in the morning of study visits but to wait until all study assessments have been completed. Subjects will receive new drug supply at each visit and will be required to bring in all unused study drugs for assessment of compliance.

Treatment Period Assessments at Visit 3 and 4 (± 3 days)

The following evaluations will be performed at each visit throughout treatment:

- Physical examination
- Anthropometric measures (Height, weight, waist circumference, BMI)
- Vital signs (pulse rate, body temperature, respiratory rate, and blood pressure)
- Blood samples for
 - lipid profile (total cholesterol, TG, HDL-C, LDL-C and LDL/HDL ratio)
 - serum chemistry (AST, ALT, CPK, BUN, serum creatinine)
- Information on adverse events
- Information on new concomitant medications
- Record of drug dispense and drug return

End of Treatment Assessments at Visit 5 (± 3 days)

The following evaluations will be performed:

- Physical examination
- Anthropometric measures (Height, weight, waist circumference, BMI)
- Vital signs (pulse rate, body temperature, respiratory rate, and blood pressure)
- Blood samples for
 - lipid profile (total cholesterol, TG, HDL-C, LDL-C and LDL/HDL ratio)
 - hematology (WBC, RBC, Hb, Hct, RDW, platelet, MCV, MCH, MCHC, neutrophil-band and segment, lymphocyte, monocyte, eosinophil, basophil)
 - serum chemistry (AST, ALT, CPK, BUN, serum creatinine, albumin, total bilirubin, direct bilirubin, ALP, total protein)
 - biomarkers (hsCRP, IL-1, IL-6, and TNF-alpha)
- 12-lead electrocardiogram
- Brachial-ankle pulse wave velocity (baPWV) and ankle-brachial index (ABI)
- Doppler color flow mapping, and CT scan of the liver for patients with confirmed fatty liver at Visit 2
- Urinalysis
 - routine urine test (pH, protein, glucose, ketone, blood, urobilinogen, bilirubin, nitrite, leukocyte)
 - clinical microscopy
- Information on adverse events
- Information on new concomitant medications
- Record of drug return

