6.2.5. Early termination visit /Withdrawal visit

For subjects who prematurely withdraw from treatment, the same procedures as the one at the end of the treatment will be applied. An end of treatment visit should be scheduled as soon as possible and the assessments listed below should be performed. Subjects will be required to bring in all study drugs for assessment of compliance. If the decision of discontinuation is being taken while the subject is in the clinic for a visit, the end of treatment assessments may be performed on that day.

- Physical examination
- Anthropometric measures (Height, weight, waist circumference, BMI)
- Vital signs (pulse rate, body temperature, respiratory rate, and blood pressure)
- Blood samples for
 - lipid profile (total cholesterol, TG, HDL-C, LDL-C and LDL/HDL ratio)
 - hematology (WBC, RBC, Hb, Hct, RDW, platelet, MCV, MCH, MCHC, neutrophil-band and segment, lymphocyte, monocyte, eosinophil, basophil)
 - serum chemistry (AST, ALT, CPK, BUN, serum creatinine, albumin, total bilirubin, direct bilirubin, ALP, total protein)
 - biomarkers (hsCRP, IL-1, IL-6, and TNF-alpha)
- 12-lead electrocardiogram
- Brachial-ankle pulse wave velocity (baPWV) and ankle-brachial index (ABI)
- CT scan of the liver for patients with confirmed fatty liver at Visit 2
- Urinalysis
 - routine urine test (pH, protein, glucose, ketone, blood, urobilinogen, bilirubin, nitrite, leukocyte)
 - clinical microscopy
- Information on adverse events
- Information on new concomitant medications

A safety follow-up should be conducted for subjects who prematurely withdraw from treatment

2 weeks after the end of treatment visit. A clinic visit is recommended unless the subject refused to return. If so, the safety follow-up may be conducted via telephone.

Subjects willing to provide information should be followed for assessments of adverse events until the end of the trial. At a minimum, the investigator should make every effort to obtain information on whether or not the subject is alive or dead at the end of the study.

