7.5. Laboratory Evaluations

7.5.1 Clinical laboratory evaluations

Laboratory tests (including hematology, biochemistry, and urinalysis) will be scheduled as below. The examination items are included in **Table 7- 1**.

Lipid Profile: Blood samples to assess total cholesterol, triglycerides, HDL-C, LDL-C, LDL/HDL ratio will be obtained from visit 1 to visit 5.

Hematology: Blood samples to assess WBC, RBC, Hb, Hct, RDW, platelet, MCV, MCH, MCHC, neutrophil-band and segment, lymphocyte, monocyte, eosinophil, basophil will be obtained at visit 2 and visit 5.

Serum Biochemistry: Blood samples to assess AST, ALT, CPK, BUN and serum creatinine will be obtained from visit 2 to visit 5, albumin, total bilirubin, direct bilirubin, ALP, total protein will be obtained at visit 2 and visit 5. At screening visit, serum creatinine shall be run for estimating glomerular filtration rate (GFR).

Urinalysis: Assessments of urine pH, protein, glucose, ketone, blood, urobilinogen, bilirubin, nitrite, leukocyte and clinical microscopy will be tested at visit 2 and visit 5.

Pregnancy Test: Urine HCG test will be performed at visit 1.

12-lead ECG: ECG will be performed in accordance with the standard procedures at the site at visit 2 and visit 5.

baPWV and ABI measurement: baPWV is used to assess arterial stiffness and will be

obtained using VP 1000 or VP 1000 plus (Omron) at visit 2 and visit 5/early termination visit. ABI is a surrogate marker of atherosclerosis and will be obtained using the same device at visit 2 and visit 5/early termination visit.

Echocardiography: Values for S', E', and A' will be measured and averaged over three consecutive cardiac cycles. A composite mean for each of these parameters is then formed by taking the average of the values from the septal, lateral, and inferior wall. The ratio of the transmitral Doppler E wave velocity and the composite mean of E' will then be used to calculate the E/E' ratio. E/E' ratio will be obtained at visit 2 and visit 5.

CT scan of the liver: Each participant will undergo non-enhanced liver computed tomography (CT) scans at visit 2. The Hounsfield Unit (HU) attenuation of liver on CT scans will be utilized for determination of fatty liver (L/S ratio <1.0 and liver attenuation <40HU). Subjects who are confirmed with fatty liver will undergo liver CT scans again at visit 5.

Table 7- 1 Laboratory tests planned to be performed

Hematology	Biochemistry	Urinalysis	Others

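### Protocol 9.5 and the SAP leave unsettled whether early-termination baPWV, ABI, E/E' and liver HU values count; read literally they are discarded, and E/E' may not be collected

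*Protocol*

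**What the plan says.** **Schedule.** The flow chart (Protocol 6.1, SAP 4.1.1) places baPWV, ABI and imaging at Visit 2 and Visit 5 only. Protocol 7.5.1 gives the same timing, with one addition: baPWV is "obtained using VP 1000 or VP 1000 plus (Omron) at visit 2 and visit 5/early termination visit", and ABI likewise. For E/E' it names Visits 2 and 5 and no early-termination measurement. For liver CT it names Visit 2, and Visit 5 if fatty liver was confirmed.

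**Early termination.** Protocol 6.2.5 opens with "For subjects who prematurely withdraw from treatment, the same procedures as the one at the end of the treatment will be applied". Its list includes baPWV and ABI, and its only imaging item is "CT scan of the liver for patients with confirmed fatty liver at Visit 2". The corresponding item in the Visit 5 list (6.2.3) is "Doppler color flow mapping, and CT scan of the liver for patients with confirmed fatty liver at Visit 2". Section 6.2.5 also allows the assessments on the day discontinuation is decided, if the patient is then in the clinic.

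**Missing-data rules.** Protocol 9.5 states "For subjects who terminate study drug early, values measured after termination of study drug will be censored" and "No missing data will be imputed for the secondary efficacy or safety analyses". SAP 7.3 repeats the no-imputation rule but has no censoring sentence. SAP 12 records no change to the protocol. Protocol 9.3 assigns the secondary efficacy analyses to the ITT population; the SAP's planned tables show these endpoints in ITT and PP.

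**The concern.** For these four endpoints a patient who stops drug before Visit 5 can have only one post-baseline value, the one from the early-termination visit. If 9.5 removes it and nothing is imputed, the patient stays in the ITT population (for example through a Visit 3 lipid result) but has no result for these endpoints. The ITT comparison then rests on patients who stayed on drug to Visit 5, which is close to what the PP analysis already shows.

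The selection may not be neutral. Protocol 4.4 expects only patients who benefit to remain and lets the investigator withdraw those who do not respond; 4.5.4 item 7 lists lack of response as a reason for withdrawal. Leaving such patients out conditions the comparison on something related to outcome. The trial would also send some withdrawing patients for a repeat CT whose efficacy result might not be used.

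**Working it through.** **1. Where each endpoint is measured**

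| Endpoint | Visit 2 | Visits 3–4 | Visit 5 | Early termination: 6.2.5 list | Early termination: 7.5.1 |
|---|---|---|---|---|---|
| baPWV, ABI | yes | no | yes | listed | named |
| Liver HU (CT) | yes | no | fatty liver only | fatty liver only | not named |
| E/E' (Doppler) | yes | no | yes | not listed | not named |

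There is no on-drug value between baseline and end of treatment. For E/E', the opening sentence of 6.2.5 implies the Doppler study, while its list and 7.5.1 leave it out.

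**2. What happens to the early-termination value**

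- *Termination means the last dose taken.* Every early-termination value comes after it and is censored. With no imputation, the patient has no post-baseline value.
- *Termination means the decision to stop.* An assessment on the day of that decision may survive; one at a later visit is censored.
- *SAP 7.3 as written.* No censoring rule is stated, so nothing removes the value. Nor does anything say it enters the analysis labelled as after 12 weeks.

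The documents do not choose among these three.

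**3. Does timing relative to dose justify discarding the value?** Dosing is once daily after the first meal (4.5.2). At on-treatment visits, including Visit 5, "subjects will be instructed not to take study drug in the morning of study visits but to wait until all study assessments have been completed". A completer who took the previous day's dose is therefore measured about one day after it. A patient who was still taking drug until the day before, and is assessed on the day discontinuation is decided, is measured at about the same interval. The difference between them is total exposure, not time since last dose.

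**4. Size.** Inputs: 20% dropout, 120 enrolled, 96 evaluable, 24 evaluable per group (Protocol 4.1 and 9.2; SAP 5); allocation 1:1:1:1.

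- The plan's dropout inflation reproduces: 24 / (1 − 0.20) = 30 per arm; 96 / (1 − 0.20) = 120.
- Expected dropouts: 0.20 × 120 = 24, and 24 / 4 = 6 per arm if spread evenly.
- Patients per arm with a post-baseline baPWV or ABI value: 24 + 6f, where f is the share of dropouts whose early-termination value is used. The same holds for E/E' if Doppler is done.

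The effect on precision, as the smallest detectable difference in SD units between two arms (normal approximation, two-sided 0.05), is (1.96 + z) × √(2/n), with z = 1.282 for 90% power and 0.842 for 80%:

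| f | n per arm | 90% power | 80% power |
|---|---|---|---|
| 0 | 24 | 3.242 × √(2/24) = 0.94 | 2.802 × √(2/24) = 0.81 |
| 0.5 | 27 | 0.88 | 0.76 |
| 1 | 30 | 0.84 | 0.72 |

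The documents do not give f, so the table shows its full range. These rows do not apply to HU: only patients with fatty liver are rescanned, and their number is not stated.

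**The case against.** A reader might infer that dropouts contribute nothing to these endpoints. The documents do not establish that. Termination of study drug is undefined, same-day assessments may not count as coming after it, 7.5.1 pairs Visit 5 with the early-termination visit as though one could stand in for the other, and the SAP does not carry the censoring sentence. What is shown is an open question whose literal answer is loss of the value.

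A reader might also infer that E/E' is excluded at early termination. It is not clearly excluded, because 6.2.5 promises the end-of-treatment procedures. This is an inconsistency between a general statement and a list.

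Nor do the documents show that dropout will depend on dose. The gastrointestinal rates in Protocol 8.2 (92.31%, 69.23%, 53.85%) are event frequencies, not withdrawal rates, and are not given by dose. Dose-related withdrawal is a possibility. The link to response has firmer support, in 4.4 and 4.5.4.

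Read at its widest, 9.5 would also remove early-termination laboratory and ECG results and the two-week safety follow-up. That cannot be intended, since 6.2.5 requires the follow-up; it shows that the sentence is too loose.

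The strongest objection is to the remedy. The objectives concern 12 weeks of treatment, and a value after a few weeks measures something else. If withdrawal differs by arm, so will exposure, and admitting only patients seen soon after the last dose adds another selection. This stands as a limit on interpretation, and is why completers must be shown separately. It does not justify leaving the rule unstated.

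**Conclusion.** The point holds as an unresolved rule with a cheap remedy. Read literally, Protocol 9.5 discards the only post-baseline baPWV, ABI and HU values of patients who withdraw early, and the ITT analyses become in effect completers-only. The SAP neither repeats nor retracts that rule. E/E' may not be collected in these patients because 6.2.5 disagrees with itself and with 7.5.1.

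At most about 6 of 30 patients per arm are affected for baPWV, ABI and E/E'. This assumes the planned 20% dropout, spread evenly, with an early-termination visit for every dropout; loss to follow-up and withdrawn consent (4.5.4) would lower it. For HU the number is smaller and cannot be derived. The loss of precision is modest, at most 0.84 to 0.94 SD in the difference detectable with 90% power. The larger concern is possible response-related selection, which the documents do not allow one to quantify. Only secondary endpoints are involved; the primary TG endpoint has its own carry-forward rule.

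**What to change.** In Protocol 9.5 and SAP 7.3, in the same words:

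1. Define termination of study drug by the date of last dose.
2. State that an early-termination assessment of baPWV, ABI, E/E' or HU made within a prespecified short interval of the last dose is used as the end-of-treatment value in the ITT analysis. Three days is an example and should be presented as a choice: the schedule's ±3 days is tolerance around a visit date, not an allowance for time off drug.
3. Limit censoring to later efficacy values, so that no safety data are removed.
4. Give completers-only results as a sensitivity analysis, and report by arm how many early-termination values were used and after how long on drug.

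In Protocol 6.2.3, 6.2.5 and 7.5.1, reconcile the Doppler item so that E/E' is collected at early termination, as 6.2.5 already promises.

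The cost is a few lines of text and no new visit. The protocol changes may need a formal amendment under 13.5, and the SAP text must be settled before database lock and unblinding. If withdrawals have already occurred without Doppler, those E/E' values cannot be recovered, but the analysis rule can still be fixed. The recovered values reflect less than 12 weeks of exposure. Patients who stop drug and return only for later visits, which Protocol 3.1 encourages, remain outside the rule.

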10. DATA HANDLING AND RECORD KEEPING

10.1. Data Management Responsibilities

Data collection and accurate documentation are the responsibility of the study staff under the supervision of the investigator. All source documents and laboratory reports must be reviewed by the study team and data entry staff, who will ensure that they are accurate and complete. Unanticipated problems and adverse events must be reviewed by the investigator or designee.

The assigned CRO will be responsible for data management, quality review, analysis, and reporting of the study data.

10.2. Investigator's File/Retention of Documents

A file for each subject must be maintained that includes the signed informed consent form and copies of all source documentation related to that subject. For each subject treated with the study drug(s), the Principal Investigator is required to prepare and maintain case histories that include all observations and other data pertinent to the investigation. This will include all source documents needed to verify the accuracy of all observations and other data contained in the Case Report Forms (CRFs) on each study patient.

The Investigator or his/her designee is required to retain the records related to the trial for a period of 2 years following the date of marketing application is approved for the indication of being investigated. If no application is to be filed or if the application is not approved for such indication, the records must still be retained until 2 years after the investigation is discontinued and the regulatory agencies are notified.

The Investigator shall retain study drug disposition records and source documents for the maximum period required by the country and the institution in which the study has been conducted, or for the period specified by the Sponsor, whichever is longer. The Investigator must contact the Sponsor prior to destroying any records associated with the study.

10.3. Source Documentation and Background Data

The investigator shall supply the REC and the authority(ies) on request with any required background data from the study documentation or clinic records. This is particularly important when CRFs are illegible or when errors in data transcription are suspected. In case of special problems and/or governmental queries or requests for audit inspections, it is also necessary to have access to the complete study records, providing protection of subject's confidentiality.

10.4. Case Report Form (CRF)

CRFs will be used for recording all data from each subject. CRFs must be typewritten or printed legibly using black ballpoint pen or completed electronically. The investigator or his/her designee is responsible for recording all data relating to the trial on the CRFs. The investigator must verify that all data entries on the CRFs are accurate and correct by signing and dating the CRFs on the designated pages.

If an item is not available or is not applicable, it should be documented as such; no blank spaces should be left on a CRF.

10.5. Data Capture Methods

Case report form (CRF) is the method for recording the data of this study. Clinical data will be written to case report forms (CRFs). All entries on the CRF are made in English and are supported by the source data.

10.6. Study Records Retention

Study documents should be retained for a minimum of 2 years after the last approval of a marketing application in an ICH region and until there are no pending or contemplated marketing applications in an ICH region or until at least 2 years have elapsed since the formal discontinuation of clinical development of the study drug. These documents should be retained for a longer period, however, if required by local regulations.

10.7. Protocol Deviations

A protocol deviation is any noncompliance with the clinical study protocol, Good Clinical Practice, or Manual of Procedures requirements. The noncompliance may be on the part of the subject, the investigator, or study staff. As a result of deviations, corrective actions are to be developed by the study staff and implemented promptly.

It is the responsibility of the site to use continuous vigilance to identify, record deviations in the "Protocol Deviation Form".

All deviations from the protocol must be addressed in study subject source documents. A completed copy of the "Protocol Deviation Form" must be maintained in the regulatory file, as well as in the subject's source document. Protocol deviations must be sent to the local REC per

their guidelines. The site PI and study staff are responsible for knowing and adhering to their REC requirements.

11. STUDY MONITORING, AUDIT AND INSPECTION

11.1. Study Monitoring

All aspect of the study will be conducted under ICH, GCP (Good Clinical Practice) guidelines and government regulations. Monitoring (by phone, fax, or on site) will be done by a representative of the study monitor designated by the sponsor. If the monitoring is done on site the monitor will check the case report forms and questionnaires for completeness and clarity, and crosscheck them with source documents. In addition to the monitoring visits, frequent communications (letter, telephone, and fax), by the study monitor will ensure that the investigation is conducted according to protocol design and regulatory requirements. Study closeout (by phone, fax or on site) will be performed by the study monitor upon closure of the study. The investigator agrees to all these monitors access to the clinical supplies, dispensing, and storage area, and to the clinical files of the study subjects, and if requested, agrees to assist the monitor.

A separate monitoring plan document should be developed to describe who will conduct the monitoring, at what frequency monitoring will be done, and at what level of detail monitoring will be conducted.

11.2. Study Audit and Inspection

In accordance with the principles of GCP, the study may be subjected to internal audits. Domestic authorities and the REC may request access to all source documents, case report forms, and other study documentation for on-site audit or inspection. Direct access to these documents must be guaranteed by the investigator, who must provide support at all times for these activities. Medical records and other study documents may be copied during audit or inspection. Subject names are obliterated on the copies to ensure confidentiality. The purpose of the audits should be to evaluate study conduct and compliance with protocol, SOPs, GCP, and the applicable regulatory requirements. The observations and findings should be documented.

12. QUALITY CONTROL AND QUALITY ASSURANCE

Quality control is the ongoing, concurrent review of data collection forms for completion and logic. Quality assurance is a comprehensive, retrospective review of all components of research records to assess adherence to protocol, standard operation procedures, and regulations, and to evaluate the accuracy of the records. Quality management is the process of assessing the quality of processes within a system and encompasses quality assurance and quality control.

For the assurance of the data accuracy, completeness, and reliability, the investigator or the study staff assigned by the investigator will evaluate the CRFs by visual review and standard computer editing to detect errors in data collection will be performed by the assigned CRO.

To protect the safety of the subjects and to ensure the data accuracy, completeness, and reliability, the research staff would preserve documented data from all sources on CRF, including lab test results, chart records, treatment conditions, physical examination, concomitant medication, and any adverse events.

